10.5.2 Treatment Facility Survey (Appendix 8)

The treatment facility survey will be completed to confirm where the patient is receiving PrEP follow up care. If they are outside of Mount Sinai Health System, they will be sent a signed authorized release form (Appendix 9).

11.0 DATA MANAGEMENT AND STATISTICAL ANALYSES

11.1 Statistical Analysis

11.1.1 General approach

Nominal and ordinal categorical variables will be summarized as frequencies and percentages. Continuous variables will be summarized with the following descriptive statistics: N, mean, standard deviation, median, minimum, maximum, interquartile range, and range.

No imputation of missing data will be performed for any of the analysis given the pilot nature of the study and small sample size.

11.1.2 Analysis of Primary and Secondary Outcomes

Analysis will be on an intention-to-treat basis. In statistical analyses, participants will be included to the date of their last active follow-up visit. Comparisons between control and experimental (iPrEP) arms. To assess the success of randomization, a summary of the baseline variables by treatment group will be tabulated and univariate comparisons performed. The primary outcome, retention in care and PrEP usage, will be compared with proportions and Fisher's exact derived confidence intervals. Secondary outcomes: Secondary analysis will focus on determining how retention in care, risk behavior, adherence or STI diagnosis differ between the groups at any of the follow-up time points. PrEP adherence based on pill counts will be calculated by dividing the number of pills taken by the number of pills prescribed. Adherence will be calculated by study month for each participant. Group adherence comparisons will be compared using Wilcoxon rank sum test. Retention in care, STI diagnosis and risk behavior at each time point will be analyzed for each study visit. Retention in care and STI diagnosis will be treated as dichotomous variables for analysis. Measures of risk behavior will include consistency of condom use and number of sexual partners since prior study visit. Condom use will be treated as an ordinal variable and number of sexual partners as a continuous variable for analysis.

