Patients will be instructed at the time of discharge that they will be contacted by a member of the PrEP Warm Line to schedule follow-up with a PrEP provider. The decision to start PrEP for those not randomized to the iPrEP arm or to stop or continue PrEP for those randomized to the iPrEP arm will be a decision made by the patient in conjunction with their PrEP provider. The ED clinical team will be available to assist patients should have they have any concerns or problems before that linkage occurs. For those randomized to the iPrEP arm if they have any side-effects within the first 14-days of starter pack use they will contact the study team and a decision to continue or stop PrEP will be made after a discussion between the patient and the PI. All patients enrolled in the study will receive standard PrEP counseling which includes information about the need for frequent HIV testing and risk reduction strategies. The importance of follow-up with the PrEP provider will be stressed. We do not anticipate the need for any re-testing (HIV, LFTs, eCrCL) by the study team after ED discharge. These tests are not typically recommended until the patient has been on PrEP for at least 30 days and sometimes not until 90-days. All recommended follow-up testing will be the responsibility of the clinical PrEP provider.

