17.2 Trial Safety

Events that would preclude a participant from continuing the intervention:

Safety concerns: Guidelines published by the Centers for Disease Control and Prevention (CDC) provide clear guidance for clinicians prescribing emtricitabine/tenofovir disoproxil fumarate or emtricitabine/tenofovir alafenamide for pre-exposure prophylaxis (PrEP). Indications for not starting or stopping PrEP once started would include renal insufficiency (eCrCL of ≤ 60 ml/min), HIV infection, Hepatitis B, pregnancy, signs or symptoms of acute HIV infection, possible HIV exposure within the last 72 hours. Indications for stopping PrEP would be a new HIV or Hepatitis B infection, worsening renal function, intolerable side effects, hypersensitivity reaction, osteopenia or pregnancy. In the group of patients randomized to iPrEP if any these safety concerns arise during the 14 days the patient is taking the PrEP starter pack they will be addressed by the PI and the patient will be withdrawn from the study since they will no longer be considered PrEP eligible.

Participants could also be removed from the study by the investigator if they do not complete any follow-up assessments within 90-days of enrollment.

Managing any medication related issues: In the group of patients randomized to iPrEP medication related side-effects that occur while the patient is taking the 14-day starter pack will be addressed by the PI. After 14-days or linkage to care (whichever occurs first) the treating PrEP provider will manage the patient as clinically indicated. For any medication related emergency we will provide a "study card" with a number to call to speak with a physician and inform patients if they need immediate treatment to go to the closest emergency room. There is no wash-out period. Patients will told to inform their treating provider of any other medications they are taking including any over-the-counter medicines. For those patients who wish to discontinue PrEP, we will recommend a test to determine HIV status at the time of discontinuation. We will also enquire about the reason for PrEP discontinuation, recent medication adherence and reported sexual risk behavior.

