18.9 Participant Withdrawal

The PI will apply his/her judgement to determine whether or not an adverse event is of sufficient severity to require that the participant be withdrawn from further study medication. A participant may also voluntarily withdraw from treatment due to what he/she perceives as an intolerable adverse event or for any other reason. If voluntary withdrawal is requested within the first 14-day and the patient was assigned to the iPrEP arm, the participant will be asked to complete an end-of-study medication visit to return unused medication and document end-of-medication outcomes.

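### Section 11.1.2 claims intention-to-treat but does not say how a participant with no day-90 status is counted, and one study-withdrawal rule is written for the iPrEP arm only

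*Combined protocol and SAP*

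**What the plan says.** The primary outcome is a yes/no state, PrEP use at 90 days (Sections 2.0 and 7.1). Three statements govern who is counted:

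- Section 11.1.2: "Analysis will be on an intention-to-treat basis".
- The next sentence: "In statistical analyses, participants will be included to the date of their last active follow-up visit".
- Section 11.1.1: "No imputation of missing data will be performed for any of the analysis".

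Section 11.1.2 then compares proportions, with confidence intervals from Fisher's exact method. It gives no denominator, and neither does the outcome list in Section 21.0.

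Several rules take people out of the study or off drug:

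- Section 17.2 lists safety concerns and continues: "In the group of patients randomized to iPrEP if any these safety concerns arise during the 14 days" of the starter pack, "the patient will be withdrawn from the study since they will no longer be considered PrEP eligible". There is no matching sentence for controls.
- Section 17.2 also says: "Participants could also be removed from the study by the investigator if they do not complete any follow-up assessments within 90-days of enrollment".
- Section 9.3 ends participation for a clinical contraindication without naming an arm, and it addresses both arms when results arrive after discharge. The samples are drawn before randomisation. Section 12.5 does the same for pregnancy.
- For side effects in the starter-pack period, Section 9.3 says "a decision to continue or stop PrEP will be made after a discussion between the patient and the PI". Section 18.9 leaves it to the PI whether an adverse event is severe enough "to require that the participant be withdrawn from further study medication". Both concern drug, not study participation.
- Section 16.0 keeps participants who miss assessments in the study, within 90 days of enrolment.

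**The concern.** A rule that includes people up to their last visit suits time-to-event or repeated-measures data. Applied to a single yes/no state at day 90, it does not say what happens to someone last seen at day 30. With imputation barred, that person has no day-90 value, and the intention-to-treat label does not supply one. Two competent analysts could report different usage rates from the same data.

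The 14-day rule adds a difference between arms. An iPrEP participant who stops for intolerable side effects in the first two weeks is withdrawn from the study. A control who starts PrEP in clinic and stops for the same reason stays in, and counts as a non-user at day 90. If the first leaves the denominator and the second does not, the iPrEP rate rises for a reason unrelated to the strategy.

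Section 17.2 itself calls loss to follow-up the main threat to validity. Aim 1b (Section 4.0) is to collect the rates needed to design the definitive trial, so the rates are what is at stake.

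**Working it through.** **The plan's own figures.** Section 11.1.3 gives power for 40 vs 40, control 50%, iPrEP 55% to 85%, two-sided pooled Z test, alpha 0.05. Exact binomial enumeration of that test at 40/40 gives 0.0812, 0.1571, 0.2859, 0.4581, 0.6474, 0.8166 and 0.9327, which matches every row to four decimals. So planning used all 80 randomised participants and no attrition. For 50% vs 80%, 34 observed per arm (85% of 40) would give 0.768 rather than 0.8166, if the rates hold among those observed.

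**Inputs below.** Arm sizes of 40 are from Section 11.1.3. The user counts, 20 control and 28 iPrEP, are assumed and correspond to its 50% vs 70% row. Withdrawal counts and the split of losses by arm are also assumed; the documents give neither.

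**Step 1: withdrawals under the 14-day rule.** Assume k withdrawn iPrEP participants, none using PrEP at day 90, leave the denominator. Difference = 28/(40 − k) − 20/40.

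| k | iPrEP | Control | Difference, points |
|---|---|---|---|
| 0 | 28/40 = 70.0% | 20/40 = 50.0% | 20.0 |
| 1 | 28/39 = 71.8% | 20/40 = 50.0% | 21.8 |
| 2 | 28/38 = 73.7% | 20/40 = 50.0% | 23.7 |

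Removing two non-users from each arm gives 28/38 − 20/38 = 21.1 points, so most of the 3.7-point shift at k = 2 comes from the rule acting on one arm. With no true effect (20 users per arm), k = 2 gives 20/38 − 20/40 = 2.6 points and k = 4 gives 20/36 − 20/40 = 5.6 points, both favouring iPrEP.

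**Step 2: general loss.** Section 17.2 expects about 85% follow-up, so take 12 of 80 lost. In the extreme case every lost participant is a non-user:

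| Lost, control/iPrEP | Observed-case difference | Points |
|---|---|---|
| 6/6 | 28/34 − 20/34 | 23.5 |
| 9/3 | 28/37 − 20/31 | 11.2 |
| 3/9 | 28/31 − 20/37 | 36.3 |

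The all-randomised difference stays at 20.0 points throughout. If 15% are lost at random instead, the expected observed-case result is 23.8/34 − 17/34 = 20.0 points: no bias.

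**Step 3: bounds on the randomised denominator.** With two iPrEP participants of unknown status and 28 known users, the difference lies between 28/40 − 20/40 = 20.0 and 30/40 − 20/40 = 25.0 points. With 6/6 unknown, it lies between 28/40 − 26/40 = 5.0 and 34/40 − 20/40 = 35.0 points.

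**Step 4: limit of counting missing as non-use.** Suppose true use is 50% in both arms and status is ascertained for 85% of iPrEP and 70% of control participants (assumed). Then 0.50 × 0.85 = 42.5% and 0.50 × 0.70 = 35.0%, a spurious 7.5 points.

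**The case against.** A reader might infer that the plan commits to an observed-case analysis under an intention-to-treat label. The documents do not support that. The label is unqualified. The power table uses the initial 40 and 40, assumes that those retained are using PrEP, and takes its control rate from clinic attendance, which implicitly makes non-attenders failures. Section 16.0 keeps people who miss assessments in the study, and Sections 9.5 and 10.5.1 allow provider or record checks, so a missed call need not mean no information. The last-visit sentence may only mean that partial data are kept. This stands: the text is ambiguous. But none of these passages states the analysis rule; the power table is expressly illustrative.

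A reader might also infer that safety withdrawals in general deplete only the iPrEP arm. That is too broad. Contraindications and pregnancy end participation in either arm (Sections 9.3 and 12.5). What remains is mainly intolerable side effects and hypersensitivity within 14 days, and the documents give no rate for these. Nor do they say that withdrawn participants leave the denominator. Removal for completing no assessments is discretionary and names no arm.

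The scale is modest too. The 3.7-point shift from two withdrawals compares with a Wald 95% half-width of 1.96 × √(0.5 × 0.5/40 + 0.7 × 0.3/40) = 21.0 points. The large swings in step 2 need every lost participant to be a non-user and loss to be uneven. The 85% anchor may itself be optimistic, since Section 11.1.3 does not expect retention in care to match the programme it comes from.

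Finally, counting missing as non-use changes the endpoint and can mislead, as step 4 shows. That argues for offering it as an option rather than requiring it.

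**Conclusion.** The point holds as an ambiguity that should be fixed, not as a demonstrated bias. No section says how unknown day-90 status counts or what the denominator is, and the stated rules do not settle it. One study-withdrawal rule covers iPrEP only, and its asymmetric part is narrow. If two withdrawn non-users left the denominator, the difference would move from 20.0 to 23.7 points; this rests on assumed counts and on their exclusion from the analysis. The bias is zero if loss is unrelated to PrEP use.

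A reader might go further and say that the trial's efficacy conclusion is compromised. Section 11.1.3 disclaims definitive efficacy, so no such decision depends on this. The consequence is for the usage and attrition rates carried into the definitive trial.

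**What to change.** **Section 11.1.2, primary outcome.** Replace the last-visit rule with a statement that all randomised participants are analysed in their assigned arm with N randomised as the denominator. Include those withdrawn or removed under Sections 9.3 and 17.2, among them patients found ineligible from samples drawn before randomisation.

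- Use provider or medical-record data (Sections 9.5 and 10.5.1) when the day-90 call is missed.
- Report n/N and missing counts by arm, so that attrition is visible separately from non-use.
- Pre-specify how unknown status counts. Missing as non-use is one option, with the caveat that ascertainment may differ by arm.
- Give observed-case and best/worst-case results alongside.

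**Section 11.1.1.** Add a matching exception to the ban on imputation.

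**Section 17.2.** Separate stopping study drug from leaving the study, so that outcomes are collected to day 90 in both arms, subject to consent. Reconcile this section with Sections 9.3 and 18.9 without changing any clinical rule.

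**Cost.** SAP wording and a small protocol amendment. Reported usage rates may be lower. If the team does not want missing counted as non-use, stating the denominator and reporting n/N with missing counts by arm still removes most of the ambiguity. The alcohol-use items in the Appendix 8 facility form are a separate issue.

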9.5 Follow-up

All follow-up assessments will be performed over the phone. Follow-up assessments will occur at 30, 60, and 90 days post enrollment.

Follow-up assessments will include:

- 1) Attitudes toward Pre-Exposure Prophylaxis Scale (APS) (Appendix 3)
- 2) Section 4 of ICAP "Screening for Substantial Risk of HIV" (Appendix 5)
- 3) Satisfaction questionnaire and qualitative assessment and visit specific satisfaction instrument (VSQ-9) (Appendix 6)
- 4) Adherence information measured by (1) self-report. Self-report will be assessed with the single measure Guidelines Regimen Information Program (GRIP) guide and questions on last dose and number of missed doses since prior follow-up. (Appendix 7)
- 5) CDC Sexual Behavior Questions (CSBQ) (Appendix 4)
- 6) STAR*D PRISE (Side-effect assessment)

Assessment of engagement in PrEP care at 30, 60, and 90 days post enrollment will be verified by direct contact with the treatment provider/program provided or by EMR review if the patient is linked within the Mount Sinai Health System. If the patient is receiving their PrEP care outside of the Mount Sinai Health System, a signed release authorization form will be sent.

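### Section 11.1.2 defines adherence by pill counts and risk behavior by partners and graded condom use between visits, but the planned telephone self-report and printed 12- or 6-month items do not yield these variables as written.

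*Combined protocol and SAP*

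**What the plan says.** **Adherence.** Section 11.1.2 states: "PrEP adherence based on pill counts will be calculated by dividing the number of pills taken by the number of pills prescribed". This is done per participant for each study month, and the arms are compared by Wilcoxon rank sum test. The same section opens with "Analysis will be on an intention-to-treat basis", and Section 11.1.1 adds "No imputation of missing data will be performed for any of the analysis".

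Section 9.5 describes the data differently: "All follow-up assessments will be performed over the phone", and "Adherence information measured by (1) self-report". The items are the GRIP rating (a single scale from excellent to very poor in Appendix 7) and "questions on last dose and number of missed doses since prior follow-up". The data-source list in Section 12.2 names only questionnaires for adherence.

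**Risk behavior.** Section 11.1.2 states: "Measures of risk behavior will include consistency of condom use and number of sexual partners since prior study visit". It continues: "Condom use will be treated as an ordinal variable and number of sexual partners as a continuous variable for analysis". Section 9.5 assigns two instruments to follow-up, the CSBQ (Appendix 4) and Section 4 of the ICAP form (Appendix 5). Section 10.4.14, however, places the CSBQ at enrollment and does not mention follow-up.

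**The concern.** The definitions and the data collection do not meet. A pill count needs someone to count pills, and a ratio to pills prescribed needs a record of the quantity prescribed. An interval partner count needs a question about the interval, and an ordinal condom variable needs graded answers. If the gap stays open, the analyst must settle these definitions outside the plan, possibly with the data in hand.

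Two consequences follow. Adherence has no value for a participant never prescribed PrEP, so with no imputation the test covers a subset formed after randomization, under a section headed by an intention-to-treat statement. Partner counts taken from long recall windows mostly describe behavior before enrollment and pull any between-arm difference towards zero. Aim 1b (Section 4.0) makes means and standard deviations of key measures a main product of this pilot, so ill-defined measures would carry into the design of the definitive trial.

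**Working it through.** The plan gives no figure for these outcomes, so there is none to reproduce. The power table in Section 11.1.3 concerns retention and PrEP use and is not touched.

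**1. Adherence: what is needed against what is described**

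- *Pills taken, by count.* Follow-up is by telephone. Return of unused medication is described only for iPrEP participants who withdraw voluntarily in the first 14 days (Section 18.9). Missed doses are self-reported (Section 9.5).
- *Pills prescribed.* No section names a source. The study supplies a 14-day pack to one arm; afterwards the treating provider manages PrEP (Section 17.2). The facility form in Appendix 8 asks about treatment of alcohol use disorder and has no quantity field.
- *Participants never prescribed PrEP.* The ratio is 0/0, and no rule is given.

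As an illustration of the subset, take the scenarios in Section 11.1.3 (40 per arm; 50% of controls and 55% to 85% of iPrEP participants retained and using PrEP), and assume only users have a value. The day-90 test then rests on 40 × 0.50 = 20 controls and 40 × 0.55 = 22 to 40 × 0.85 = 34 iPrEP participants.

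**2. Risk behavior: recall windows**

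Inputs: the CSBQ partner item covers 12 months (365 days); the ICAP Section 4 prompt covers 6 months (182.5 days); calls fall at d = 30, 60 and 90. With window W, the pre-enrollment share is (W − d)/W. Assuming a constant rate of new partners, each counted once, a true 50% fall after enrollment shows as 0.5 × d/W.

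| d | Before enrollment, 12 months | Before enrollment, 6 months | 50% fall seen, 12 months | 50% fall seen, 6 months |
|---|---|---|---|---|
| 30 | 335/365 = 91.8% | 152.5/182.5 = 83.6% | 4.1% | 8.2% |
| 60 | 305/365 = 83.6% | 122.5/182.5 = 67.1% | 8.2% | 16.4% |
| 90 | 275/365 = 75.3% | 92.5/182.5 = 50.7% | 12.3% | 24.7% |

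The 6-month columns also assume that the number given to the prompt is written down; the form itself shows a tick box.

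Subtracting consecutive counts does not recover the interval count. At 12 partners a year before enrollment, and a fraction f of that rate afterwards, the 12-month count at day 30 is 12 × 335/365 + f × 12 × 30/365. This gives 12.0, 11.5 and 11.0 for f = 1, 0.5 and 0. The changes from enrollment are 0, −0.5 and −1.0, while the true interval counts are 1.0, 0.5 and 0.

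For condoms, the CSBQ asks yes/no about the last act, and the ICAP prompt on consistent use has no graded answer.

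**3. Test of a replacement adherence formula**

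Take (days on PrEP − missed doses)/days on PrEP, counted from the later of PrEP start and last completed contact.

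- A control starts on day 14, misses the day-30 call and is reached on day 60: 60 − 14 = 46 days. Perfect dosing gives 46/46 = 100%, and 90% dosing gives 41.4/46 = 90%. Dividing by all 60 days since last contact would give 46/60 = 77% and 41.4/60 = 69%.
- An iPrEP participant finishes the 14-day pack and stops, with calls on days 30 and 60. The first interval gives 14/14 = 100%. In the second, the last dose (day 14) precedes the last contact (day 30), so the denominator would be 14 − 30 = −16 days. The formula needs an explicit rule for this case.

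**The case against.** The strongest reply is that this is largely loose wording in exploratory outcomes of a pilot that declares itself underpowered, and that the data could still be assembled. Much of that stands.

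- **Sources may exist.** A reader might infer that pills prescribed and control start dates cannot be obtained at all. The documents do not support that. The engagement survey under Outcome Data (second Section 10.5.1) asks about PrEP use at each time point and is confirmed with the provider or record; its form is not printed, so its content is unknown. Sections 9.5, 12.1.2 and 17.2 provide for record review, and question 3 of Appendix 8 asks when care began. What remains is that no section assigns any of these to adherence, and start of care need not be start of PrEP.
- **Intention-to-treat.** A reader might infer that the plan disguises a subset analysis. Sections 7.2 and 21.0 already describe adherence as following PrEP initiation. The gap is that Section 11.1.2 does not carry that condition into the analysis.
- **Condom and timing items.** The second tier of the CSBQ has act-level condom items by partner type and month and year of last sex. An ordered score could be built, and many last acts could be dated relative to enrollment. The plan specifies no such score, and last-act answers do not measure consistency over an interval.
- **Size of the dilution.** Quoting only the 12-month figures would overstate it; on the 6-month prompt it is about half as severe. If Section 10.4.14 governs, the CSBQ is not repeated and its 12-month arithmetic does not apply at follow-up.

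**Conclusion.** The mismatch holds. Following Section 11.1.2 literally, neither the pill-count ratio nor the interval risk variables can be produced from the methods and printed items described. Adherence can be approximated from self-report once its definition and start dates are fixed. Interval partner counts cannot be derived from the long-recall items: the window is 92%, 84% and 75% pre-enrollment time on the 12-month item, and 84%, 67% and 51% on the 6-month prompt. A true 50% fall would appear as about 4%, 8% and 12%, or 8%, 16% and 25%, given a constant rate of new partners. The adherence counts of 20 against 22 to 34 are illustrative only.

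A reader might infer that the trial's main result is at risk. It is not: the primary outcome, PrEP usage at 90 days, does not use these variables. The change is worth making because it is cheap and because these measures are meant to inform the next trial.

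**What to change.** **Adherence**

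- Remove the pill-count wording. Define adherence per interval as (days on PrEP − self-reported missed doses)/days on PrEP. Count from the later of PrEP start and last completed contact, to the assessment, or to the last dose if the participant has stopped.
- If the last dose precedes the last contact, or PrEP was never started, assign no value and count the participant by arm as stopped or never started.
- Record the PrEP start date in both arms at follow-up.
- Label the comparison as *among participants on PrEP in the interval*, not intention-to-treat. Report by arm the denominator days and the numbers never started, stopped, withdrawn or not reached.
- Keep PrEP usage in all randomized participants as the intention-to-treat outcome.

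**Risk behavior**

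- At follow-up, ask for partners and graded condom-use frequency (never to always) since the last study contact; ask the same items over 30 days at enrollment.
- Analyze partners per 30 days, because Section 16.0 keeps participants who miss calls and intervals will vary.
- Reconcile Sections 9.5 and 10.4.14 on whether the CSBQ is repeated.

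**Cost.** SAP rewording, a few revised REDCap items, an IRB amendment, and departure from the original instrument wording. The adherence comparison is not protected by randomization and does not capture stopping, as the 14/14 example shows; the counts by arm and the PrEP usage outcome do. A control starting on day 14 contributes 30 − 14 = 16 days in month 1 against 30, which is why denominator days are reported.

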To maximize retention we will use a Locator Form to collect the study participants current address, email address, phone numbers and, with consent, private social media information. In order to facilitate linkage and follow-up, we will also collect similar information for friends and family who know how to reach the patient. All follow-up assessments will be conducted at 30, 60, and 90 from PrEP initiation. All follow-up assessments will be conducted by telephone. Patients will be mailed an appointment reminder and receive a phone call a week and a day before their scheduled assessment. Patients who miss one or more than one follow-up assessment will continue in the study so long as it is within 90 days of their enrollment.

We will provide a \$25 cash incentive for all participants to complete their enrollment, 30, 60 and 90-day follow-up assessments.

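### Recall back to the preceding contact has no fixed length: a call completed after a missed one can cover 60 or 90 days, the plan has no rule for this, and its listed forms do not match the variables it analyses

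*Combined protocol and SAP*

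**What the plan says.** Timing and mode (Section 9.5): "Follow-up assessments will occur at 30, 60, and 90 days post enrollment", and "All follow-up assessments will be performed over the phone".

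Missed calls (Section 16.0, where the 90 days run from enrollment): "Patients who miss one or more than one follow-up assessment will continue in the study so long as it is within 90 days of their".

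Adherence: Section 9.5 collects self-report only, by the GRIP item and "questions on last dose and number of missed doses since prior follow-up". Section 11.1.2 analyses something else: "PrEP adherence based on pill counts will be calculated by dividing the number of pills taken by the number of pills prescribed", followed by "Adherence will be calculated by study month for each participant".

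Risk behavior (Section 11.1.2): "Measures of risk behavior will include consistency of condom use and number of sexual partners since prior study visit". The comparison is made visit by visit: "Retention in care, STI diagnosis and risk behavior at each time point will be analyzed for each study visit". Partner number is treated as continuous. No rate, offset, interval date or test is given for it.

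Forms: Section 9.5 lists the CSBQ (Appendix 4) and Section 4 of the ICAP form (Appendix 5) at follow-up. The CSBQ asks for the number of partners over 12 months, and the ICAP form over 6 months.

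The plan does not say whether the prior visit is the last one completed or the last one scheduled.

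**The concern.** If the window opens at the last completed contact, its length depends on which calls were answered. A day-90 report covers 30 days after a completed day-60 call, 60 days if only day 60 was missed, and 90 days if days 30 and 60 were both missed. Section 11.1.2 would put these reports into one visit-level comparison as though they covered equal time. The no-imputation rule in Section 11.1.1 does not help, because a long-window count is an observed value.

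Aim 1b and Section 11.1.3 say the pilot is to supply means and standard deviations for planning a definitive trial. Values that depend on this pilot's pattern of answered calls are poor planning inputs, even if both arms answer equally often. If the arms differ in call completion, part of any difference in partner number could reflect window length alone.

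**Working it through.** **The plan's own figure.** The plan gives no figure for window length. Its only calculated design figure is the power table in Section 11.1.3. Exact enumeration of the two-sided pooled Z test with 40 per arm reproduces all seven powers to four decimals. The table concerns retention in care and PrEP use and is not in question here.

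**Inputs.** Calls at days 30, 60 and 90 (Section 9.5). Expected follow-up of 85% (Section 17.2). Assumptions: each call is completed independently with probability q, calls fall on the scheduled day, and the window opens at the last completed contact.

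**Window length among those who complete the call.**
- Day 60: 30q + 60(1−q). At q = 0.85: 25.5 + 9.0 = 34.5 days (+15%).
- Day 90: 30q + 60q(1−q) + 90(1−q)². At q = 0.85: 30(0.85) + 60(0.1275) + 90(0.0225) = 25.5 + 7.65 + 2.03 = 35.2 days (+17%). The share with more than 30 days is 12.75% + 2.25% = 15%.
- Range for day 90: 41.7 days (+39%) at q = 0.70 and 52.5 days (+75%) at q = 0.50.

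**Who is affected.** At q = 0.85, 1 − 0.85³ = 38.6% miss at least one call. The patterns with no long-window report are: all three completed (0.6141), only day 90 missed (0.1084), days 60 and 90 missed (0.0191), and all missed (0.0034). They sum to 0.745, so 25.5% give at least one long-window report.

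**Partner counts, no true arm effect.** Assume over-dispersed (gamma-Poisson) counts with mean 2 per 30 days and SD about 2.4, proportional to window length, with 40 per arm and 4,000 simulated trials. The Wilcoxon test is also an assumption, since the plan names it only for adherence.
- 85% completion in both arms: the day-90 mean is 2 × 1.1725 = 2.3 and the SD about 2.9. The false-positive rate stays near 5%.
- 85% vs 70%: the ratio of means is 41.7/35.2 = 1.19 and the false-positive rate about 7% (about 11% without over-dispersion).
- Dividing each count by its own window returns the rate to about 5%.

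Proportionality makes these upper bounds, because a repeat partner counts once. If only half the count grows with time, 85% vs 70% gives about 5%.

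**Adherence.** Take 5 missed doses per 30 (assumption), a true value of 25/30 = 83.3%. Over 60 days with 60 prescribed, the ratio is 50/60 = 83.3%, unchanged. Only if the 60-day count of 10 missed is set against 30 prescribed does it fall, to 20/30 = 66.7%. The matched ratio is therefore sound. However, one 60-day total does not say how the 10 missed doses divide between the two study months, and Section 11.1.2 requires monthly values.

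**Forms against analysis.** At day 90 the 12-month item reaches back 12 − 3 = 9 months before enrollment, and the 6-month item 6 − 3 = 3 months. At day 30 the figures are 11 and 5 months. Neither yields a count since the prior visit.

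**The case against.** The strongest reply is that the stretched partner count would never be collected. The printed questions have fixed recall, so all respondents answer over the same period. That is right for the forms as printed, but it replaces one fault with another: Section 11.1.2 analyses a variable that no listed form produces, and the printed recall mixes pre- and post-randomization behavior.

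Second, a reader might infer that missing calls pushes a 90% adherer down to 80% and then 70%. The documents do not support this. The stated denominator is pills prescribed, and the fall occurs only if that is held to one month while the numerator is not. Such a calculation would even give 1 − 0.4 × 3 = −20% for a true 60% adherer over 90 days. What stands is that the total cannot be split by month, and that Section 11.1.2 relies on pill counts while Section 9.5 lists phone self-report.

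Third, a reader might infer that everyone who misses a call is mis-scored. Those who complete no later call contribute no long-window report; at 85% completion that is about a third of those who miss any.

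Fourth, a large arm bias can be produced by assuming 85% completion in one arm and 50% in the other (false-positive rate about 14% with over-dispersed counts). The documents give no basis for that split. The 50% figures are follow-up in an HCV program without locator data or facilitated linkage, and assumed control-arm retention in care. Both arms here receive the same linkage, locator form, reminders and payment.

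Finally, the prior visit might mean the last scheduled one. The plan does not say, and that needs settling in any case.

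**Conclusion.** The concern holds in a limited form. Sections 9.5 and 11.1.2 rely on recall of no fixed length, Section 16.0 retains participants who miss calls, and nothing says how a report spanning a missed call enters the visit-level partner comparison or the monthly adherence values. If the window opens at the last completed contact and 85% of calls are completed independently, 15% of day-90 respondents report over more than 30 days and the mean window is 17% too long, an upper bound for partner inflation.

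The consequence that does not depend on a difference between arms is distortion of the pilot's means and SDs. Bias in the arm comparison requires unequal call completion and is small at 85% vs 70%. The mismatches between the analysis text and the follow-up measures (partner recall period, pill counts) stand on the text alone and need no assumption about missed calls.

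Only secondary outcomes are affected. A reader should not extend this to the primary outcome, PrEP use at 90 days, or to the power table. The point is worth correcting because the remedy is cheap and improves the plan under every reading.

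**What to change.** In Sections 9.5 and 11.1.2, use one fixed item covering the past 30 days for missed doses and one for number of partners, asked at every call whether or not the previous call was completed. The partner item must be added, or the CSBQ or ICAP item altered for follow-up, because no existing question asks about partners since the prior visit. Leave a month with no completed call missing. Replace the pill-count wording with adherence from self-reported missed doses over pills prescribed in the same 30 days.

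Alternatively, keep the open window but define the prior contact as the last completed one and record its date. Compute adherence over that actual interval rather than by study month, with pills prescribed over the same interval as denominator. Analyse partners per 30 days or with log(days since last completed contact) as an offset.

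The cost is a change to the follow-up form and a few sentences of analysis text, with no extra participants or calls. The downside of the fixed window is that events more than 30 days back are not captured for participants who missed calls.
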